## **10.2. Exposure variables**

- 1) Total area of available floor space inside the home (m^2)
- 2) Frequency that child plays outdoors
- 3) Total number of physical hazards in the home (presence of open stairwells, stove height)
- 4) Total number of fine-motor activity items available to the child
- 5) Presence of gross-motor activity items available to the child across each category (e.g., fixed, portable: ball equipment, push/pull equipment, riding equipment, rocking and twisting equipment)
- 6) Hemoglobin concentration (g/L).

Descriptions and derivations of each of these variables can be found in Table 1 (Appendix).

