In addition, we will be using the GPS logging data to create ‘heat maps’ for each of the participants’ physical activity locations. This will first be done at the individual level using kernel density estimation and smoothing. These individual ‘heat maps’ can be combined in a master map that will create a visual piece that can aid in describing study findings. We will then use the heat maps for each individual to estimate the average diameter of the ‘sphere’ of activity (km) for the entire study population.

***Objective #2:*** *Estimate the associations between characteristics of the physical environment of the home environment (total area of available floor space inside of the home; frequency that child plays outdoors; number of physical hazards present within the home; number of stationary gross-motor activity-facilitating items present; and number of portable gross-motor activity-facilitating items present) and preschooler activity level.*

To address our second objective, we will first graph each of the variables of interest to assess the data for outliers or implausible data. We will generate histograms, box-plots, and Q-Q plots to assess the following continuous variable:

- Total area of available floor space inside of the home (m^2); Height of stove inside the home (m);

We will generate medians and IQRs for the following discrete, continuous variables:

- Open stairwells in the home (no railing);
- Presence of fine-motor activity-facilitating items;
- Presence of gross-motor activity-facilitating items (for each category).

These discrete, continuous variables may be categorized and treated as categorical variables depending on the data. To assess the linearity between these continuous exposures and outcome measure (using each parameter defined in Section 10.1.), we will create scatterplots and generate the correlation coefficient (Pearson correlation) for each relationship. A locally weighted scatterplot smoother (LOWESS) technique will also be used to check for departures from linearity. If the association between the exposure and the outcome is linear, we will proceed with the linear regression. However, if the association is non-linear, we will proceed with a linear spline model.

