***Descriptive statistics:***

We will calculate the mean and standard deviation of the following continuous measures:

- Area of available floor space indoors;
- Population density of indoor space (number of people dwelling in the home/total available area of indoor floor space);
- Height of stairwell railings (of those that had a railings); and

- Height of stove (of those who had stoves)

We will estimate the median and interquartile range of the following discrete measures:

- Number of rooms within the homes;
- Number of people who live in the home

We will generate tabular descriptions (frequencies and percents) of the following measures:

- Homes that had open stairwells (no railings);
- Homes that had minor (<1m^2) unfinished construction (of those who had unfinished construction);
- Those who had major (>1m^2) unfinished construction (of those who had unfinished construction);
- Building materials that the activity-facilitating items in the home are made of (e.g., clay, plastic, metal, wood, cloth, other).

We will use a mixed linear model with a random child-specific intercept. This is due to the repeated measures collected over the 7-day period for each participant. The physical activity data will be analyzed in activity counts per 15 second epochs, however to create multiple observations, we will nest the data by averaging the epochs over each of the 7 days to create 7 separate observations in each of the participant's datasets. This method was chosen since it will appropriately model the means and standard errors as well as properly handle missing data. We will use this model to estimate the unadjusted and multivariable-adjusted associations between each of the exposure variables (specified above) and PA level (counts/15s). Covariates that will be included in multivariable models will be pre-determined using a hypothesized directed acyclic graph (DAG).

***Objective #3: Estimate the associations between haemoglobin concentration (Hb) and preschooler physical activity level.***

To address our third objective, summary statistics (including mean, standard deviation, median, range, interquartile range) will be generated for hemoglobin (as a continuous variable) to help identify outliers and biologically implausible data.

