
outside of the home
		
 
• Averages of the 2 length measures from each enclosed space outside the home (m)
 
• Averages of the 2 width measure from each enclosed space outside the home (m)
 
• Averages of the 2 length measures from each large obstruction (>1m^2) within the enclosed space outside of the home (m)
 
• Averages of the 2 width measures from each large obstruction (>1m^2) within the enclosed space outside of the home (m)
 
 
Area of the enclosed outdoor space will be calculated by multiplying the averages of the 2 length by width measures for each outdoor space (m^2). Area of each large obstruction outdoors will be calculated by multiplying the averages of the 2 length by width measures for each large obstruction within the enclosed outdoor space (m^2).
 
The total area of enclosed outdoor space (m^2) will be calculated by summing all of the averages of enclosed outdoor space. The total area of large obstructions (m^2) will be calculated by summing all of the areas of large obstructions within the enclosed outdoor space outside of the home. Finally, the area of total available floor space outside of the home (m^2) will be calculated by subtracting the total area of large outdoor obstructions (m^2) from the total area of enclosed outdoor space (m^2).
 
Finally, the summation of the total available floor space inside of the home (m^2) and the total available floor space outside of the home (m^2) will provide the total available floor space inside and outside of the home (m^2).

Total number of physical hazards in or around the home
	
Count (all integers between 0 and 5); discrete
	
Data required:
 
 
• Presence of unsafe stairwell (No = 0; Yes = 1)             
 
○ Form 3: Questions 12a, 12b, 12c, and 12d
 
○ “No” (will receive a score of 0) if:                 
 
▪ Q12a = 1
 
 
 
 
 

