		
 
 
 
▪ Q12a = 2; Q12b = 2; Q12c >0.9 m; Q12d = 1
 
▪ Q12a = 2; Q12b = 2; Q12c >0.9 m; Q12d = 2
 
 
 
○ “Yes” (will receive a score of 1) if:           
 
▪ Q12a = 2; Q12c <0.9 m; Q12d = 1
 
▪ Q12a = 2; Q12c <0.9 m; Q12d = 2
 
▪ Q12a = 2; Q12c >0.9 m; Q12d = 1
 
 
 
● Presence of stove that is accessible to child (No = 0; Yes = 1)           
 
○ Form 3: Questions 13a and 13b
 
○ “No” (will receive a score of 0) if:               
 
▪ Q13a = 1
 
▪ Q13a = 2; Q13b >0.9 m
 
 
 
○ “Yes” (will receive a score of 1) if:               
 
▪ Q13a = 2; Q13b <0.9 m
 
 
 
 
 
● Presence of unfinished construction (No = 0; Yes = 1)           
 
○ Form 3: Question 14
 
○ “No” (will receive a score of 0) if:               
 
▪ Q14 = 1
 
 
 
○ “Yes” (will receive a score of 1) if:               
 
▪ Q14 = 2
 
▪ Q14 = 3
 
 
 
 
 
● Presence of uncovered sewage drain, accessible to the child (No = 0; Yes = 1)           
 
○ Form 3: Question 15
 
○ “No” (will receive a score of 0) if:               
 
▪ Q15 = 1
 
 
 
○ “Yes” (will receive a score of 1) if:               
 
▪ Q15 = 2
 
 
 
 
 
● Presence of boti in home and storage of item is accessible to the child (No = 0; Yes = 1)           
 
○ Form 3: Questions 16a and 16b
 
○ “No” (will receive a score of 0):               
 
▪ Q16a = 1
 
▪ Q16a = 2; Q16b = 2
 
 
 
○ “Yes” (will receive a score of 1):
 
 
 

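### The stairwell rows of the hazard score are not exhaustive: a stairwell with no recorded railing height, and a railing or stove at exactly 0.9 m, match no scoring row

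*Combined protocol and SAP*

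**What the plan says.** Section 10.2 lists the hazard count as an exposure and describes it by two of its components: "Total number of physical hazards in the home (presence of open stairwells, stove height". Section 10.4.1, Objective 2, treats a stairwell as open when it has no railing, first among the variables to be summarised ("Open stairwells in the home (no railing") and again among the tabulated home characteristics ("Homes that had open stairwells (no railings"). Railing height is described only for a subset: "Height of stairwell railings (of those that had a railings); and".

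Section 10.2 refers to Table 1 of the Appendix for the derivation. There the stairwell item, "Presence of unsafe stairwell (No = 0; Yes = 1", is built from "Form 3: Questions 12a, 12b, 12c, and 12d". It has three rows that score 0 and three that score 1. The stove item uses Q13a and Q13b, with the same 0.9 m limit. The total is the plain sum of five 0/1 items. The table does not say what happens when an item cannot be scored.

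**The concern.** A scoring rule for an exposure should give each possible answer exactly one score. This one appears to leave out the case the plan describes as the hazard, because all stairwell rows that apply when a stairwell exists depend on a railing height. A home with open stairs may have no such height.

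If the rule is coded literally, the item is then either missing, which makes the total missing, or 0 by default. In the second case a home with open stairs scores one point lower than an otherwise identical home with a low railing, which runs against the plan's own notion of the hazard. The score is one value per child, so the mixed model's tolerance of missing days does not help: a child with no total has no exposure value on any day.

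**Working it through.** There is no stated figure to reproduce; the check is a logical one on the rows of Table 1.

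**Rows as written, stairwell item**

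| Score | Q12a | Q12b | Q12c | Q12d |
|---|---|---|---|---|
| 0 | 1 | not used | not used | not used |
| 0 | 2 | 2 | above 0.9 m | 1 |
| 0 | 2 | 2 | above 0.9 m | 2 |
| 1 | 2 | not used | below 0.9 m | 1 |
| 1 | 2 | not used | below 0.9 m | 2 |
| 1 | 2 | not used | above 0.9 m | 1 |

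**Every pattern for a home with a stairwell (Q12a = 2), Q12d answered**

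| Q12c | Q12b = 1, Q12d = 1 | Q12b = 1, Q12d = 2 | Q12b = 2, Q12d = 1 | Q12b = 2, Q12d = 2 |
|---|---|---|---|---|
| blank | no row | no row | no row | no row |
| below 0.9 m (including 0 m) | 1 | 1 | 1 | 1 |
| exactly 0.9 m | no row | no row | no row | no row |
| above 0.9 m | 1 | no row | both 0 and 1 | 0 |

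Of the 4 × 4 = 16 patterns, 4 + 4 + 1 = 9 match no row, 4 + 1 = 5 score 1, 1 scores 0 and 1 scores both. These are answer patterns, not homes, and some may never occur. If Q12d is blank as well, no row matches at any height.

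**Stove item, stove present (Q13a = 2):** 0.8 m scores 1, 1.0 m scores 0, 0.9 m matches no row.

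**How this bears on open stairwells.** The meaning of the codes has to be inferred. Apart from homes with no stairwell, a score of 0 needs Q12b = 2 together with a height above 0.9 m, which fits a railing that is present and high enough. The descriptive statistics need both railing presence and railing height, and Table 1 lists only Q12a to Q12d for stairwells. On that reading the result turns on what was entered in Q12c when there was no railing:

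- Q12c blank: no row matches, whatever Q12b and Q12d hold. The total is missing, or one point too low on a 0-5 scale if the item defaults to 0.
- Q12c = 0 m and Q12d answered: the home scores 1, as intended.
- Q12c = 0 m and Q12d blank: no row matches.

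**Whether another part of the plan closes the gap.** The missing-data procedure in section 10.4.1 covers values that were missed and can be re-collected, and measures the family declined. A height that does not apply is neither.

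**The case against.** The strongest reply is that Form 3 is not available, so a blank Q12c is an inference. If staff entered 0 m for a stairwell with no railing, the score-1 rows, which do not use Q12b, catch it correctly. The restriction of railing height to homes with a railing ("Height of stairwell railings (of those that had a railings") does not settle this: it fits blanks, but it also fits zeros that have to be kept out of a mean. This stands, and the open-stairwell half of the point is therefore conditional. What remains is that the plan states no such convention, and the score depends on one.

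The reading of Q12b can also be questioned. One score-0 row and one score-1 row differ only in whether Q12b = 2 is stated, so either the rows are faulty or Q12b means something else. This too is fair, but the gap for an absent height does not depend on Q12b, because every row with a stairwell needs a height.

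It can be added that open stairwells are tabulated separately, so affected homes could be found and corrected from data already collected, and that the stairwell is only one of five items. Both are true. They make the repair cheap and limit the reach of the fault; they do not supply the missing rule.

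A reader might go further and infer that the exposure contrast in Objective 2 is reversed, or that a particular number of the 60 children is lost. The documents support neither. They do not say how common open stairwells are, and no calculation in them bears on the direction of the association.

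**Conclusion.** The point holds in a limited form. It is certain from the text that the stairwell rows do not cover an absent railing height, that exactly 0.9 m is unscored for both railing and stove, and that one pattern meets a score-0 and a score-1 row at once. It is conditional that open stairwells go unscored: this needs Q12b to be railing presence and Q12c to be blank when there is no railing.

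Where that condition is met, each affected home has a missing total or one that is one point too low out of five. A reader might assume that the total is also too low at exactly 0.9 m. That does not follow, because the plan does not say on which side of the limit 0.9 m falls; the item there is simply unscored.

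The number of affected homes is unknown. The consequence is possible misclassification or loss of homes in the hazard-count exposure of Objective 2, and in any description of that count. The activity estimate of Objective 1 and the sample size are not touched.

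**What to change.** Rewrite the stairwell rows of Table 1 so that they are mutually exclusive and exhaustive, and state in the table what the codes of Q12a to Q12d mean. In one edit:

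- Score a stairwell with no railing as 1, whatever Q12c and Q12d hold.
- Assign exactly 0.9 m to one side of the limit, for both railing and stove.
- Reconcile the overlap at Q12a = 2, Q12b = 2, Q12c above 0.9 m, Q12d = 1, and say what Q12d contributes. Changing only the height limit is not enough: a rule that any railing of at least 0.9 m scores 0 would contradict the existing score-1 row for heights above 0.9 m with Q12d = 1.
- State how an item that still cannot be scored enters the total.

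The cost is a revision of the stairwell and stove entries in one table, made before the score is coded. If Form 3 records railing presence, as the planned tabulation of open stairwells implies, no new data are needed.

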Next, the study personnel will ask about any outdoor spaces that are accessible to the child. Only outdoor spaces that have clear perimeters (e.g., fenced in backyard, railings or walls surrounding a rooftop, railings surrounding a balcony) will be measured using the laser-measuring device. If the laser does not operate in the outdoor environment (e.g., weather conditions do not permit the proper lighting standards necessary to obtain a reading), a standard tape measure will be used. Open streets, alleyways, large parks or green spaces, or outdoor spaces that do not have a clear perimeter will not be measured; however, they will be documented and physical characteristics will be described by study personnel in the

appropriate sections of Form 3. Study personnel will be asked to photograph all outdoor spaces, consent permitting, as long as they do not include any individuals within the pictures.

Once the indoor, and if applicable, outdoor area has been measured, the study personnel will assess the home environment for physical hazards. Using the audit provided (Form 3), they will assess the presence and safety surrounding stairwells, accessibility to stovetops and open sewage drains, as well as the presence of unfinished construction and common household hazards (e.g., boti, a common household cutting device in Bangladesh). A check list will be provided to the caregiver at the final visit which will indicate if any of the 5 hazards that we are assessing are present in their home. In addition, we will provide them with strategies to increase safety of their children (e.g., put up railing around stairwells, keep boti in a space that isn't accessible to the child, etc.).

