### **10.4. Statistical Analysis**

#### **10.4.1. Primary Analysis**

Statistical analyses will be performed using STATA (College Station, TX). Data from Forms 1, 2, 3, 4, and the Accelerometry and GPS Log will be double entered in real time independently by research personnel. Data forms will be de-identified, such that only a participant ID number will be used to identify participants. Any discrepancies between data enterers will be flagged and reconciled by the student investigator. Data reconciliation will be conducted by the student investigator and will consist of reviewing the original hardcopy of the document and/or discussing the measure with the research assistant who had originally recorded it. Data review will consist of creating histograms, boxplots, and normal quantile-quantile (Q-Q) plots of each continuous variable to identify outliers and potentially implausible data.

Each day, the student investigator will assess the hardcopies of the data collection forms for missing data. In the case that data that can be collected over the telephone is missing (e.g., socioeconomic information, age, home perception questionnaire measures, etc.), if the missing data is flagged within 60 days of the date of initial collection, study personnel will reach out to the participant and their caregiver via telephone call to collect the measure of interest. If the missing data is flagged outside of the 60-day window of re-collection, the participant will be automatically opted out of that particular measure. In the case that data that must be collected in person is missing (e.g., body composition measures, dimensions of the home environment, hemoglobin concentration, etc.), if the missing data is flagged within 21 days of the date of initial collection, study personnel will reach out to the participant and their caregiver to schedule another home visit to collect the measure of interest (e.g., if measures are missing from the initial home visit, they may be collected in person during the final visit). In the case that the participant or their caregiver has opted out of a particular measure (e.g., hemoglobin concentration), they will not be included in analyses that involve that measure of interest.

**Objective #1:** Describe physical activity levels of the sample of preschoolers in urban Dhaka.

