--	--	--------------------------------------------------------------------------------------------------------------------------------------------------------------------------------------------------------------------------------------------------------------------------------------------------------------------------------------------------------------------------------------------------------------------------------------------------------------------------------------------------------------------------------------------------------------------------------------------------------------------------------------------------------------------------------------------------------------------------------------------------------------------------------------------------------------------------------------------------------------------------------------------------------------------------------------------------------------------------------------------------------------------------------------------------------------------------------------------------------------------------------------------------------------------------------------------------------------------------------------------------------------------------------------------------------------------------------------------------------------------------------------------------------------------------------------------------------------------------------------------------------------------------------------------------------------------------------------------------------------------------------------------------------------------------------------------------------------------------------------------------------------------------------------------------------------------------------------------------------------------------------------------------------------------------------------------------------------------------------------------------------------------------------------------------------------------------------------------------------------------------------------------------------------------------------------------------------------------------

		
 
▪ Q16a = 2; Q16b = 1
 
 
Each score from each of the 5 categories will be added to calculate the combined total of hazards present in the home.

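### Table 1 scores one stairwell answer pattern as both 0 and 1, and gives a height of exactly 0.9 m no score, so the hazard count is ambiguous or undefined for homes with those answers

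*Combined protocol and SAP*

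**What the plan says.** Section 10.2 lists the total number of physical hazards as an exposure and names open stairwells and stove height as examples. Section 10.4.1 (Objective #2) relates it to activity in a mixed linear model. Its operational definition is in Table 1 of the Appendix: five items scored 0 or 1, with "Each score from each of the 5 categories will be added to calculate the combined total of hazards present in the home".

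The stairwell item uses Form 3 questions 12a to 12d. It scores 0 if Q12a is 1, or on either of two longer lines, one of which is "Q12a = 2; Q12b = 2; Q12c >0.9 m; Q12d = 1"; the other differs only in having Q12d equal to 2. It scores 1 on any of three lines, the third being "Q12a = 2; Q12c >0.9 m; Q12d = 1". None of the three lines scoring 1 mentions Q12b.

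The stove item scores 1 for "Q13a = 2; Q13b <0.9 m" and 0 when there is a stove higher than 0.9 m.

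Other sections touch on the same hazards without giving a scoring rule. Section 9.3.4 plans a caregiver check list to "indicate if any of the 5 hazards that we are assessing are present in their home", but does not say that it applies the Table 1 rule. Section 10.4.1 separately tabulates open stairwells and summarises railing and stove heights. Its re-collection step for in-person measures applies "if the missing data is flagged within 21 days of the date of initial collection" and concerns absent data only.

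**The concern.** A scoring rule should give each possible set of answers exactly one score. Here one fully answered stairwell pattern appears to fall in both lists, and one height value falls in neither, for two of the five items. Two analysts following Table 1 faithfully could then build different hazard counts from the same forms, or find that the five-item sum cannot be formed for a home. If the choice were made after the activity data had been seen, it would be an unplanned decision about an exposure.

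**Working it through.** **Step 1. Code the stairwell rule literally.** Inputs are the Table 1 lines. With Q12a = 2:

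- Score 0 if Q12b = 2, Q12c > 0.9 m and Q12d is 1 or 2.
- Score 1 if Q12c < 0.9 m and Q12d is 1 or 2, whatever Q12b is.
- Score 1 if Q12c > 0.9 m and Q12d = 1, whatever Q12b is.

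Enumerating every complete answer set (2 × 3 × 2 = 12 patterns):

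| Q12b | Q12d | Q12c < 0.9 m | Q12c = 0.9 m | Q12c > 0.9 m |
|---|---|---|---|---|
| 1 | 1 | 1 | none | 1 |
| 1 | 2 | 1 | none | none |
| 2 | 1 | 1 | none | **0 and 1** |
| 2 | 2 | 1 | none | 0 |

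Exactly one pattern has two scores. All four patterns at exactly 0.9 m have none. Away from 0.9 m, 6 of 8 patterns have a single score, one has two and one has none. When Q12a = 1 the score is always 0.

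**Step 2. The stove item.** With a stove present, below 0.9 m scores 1, above scores 0, and exactly 0.9 m has no score.

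**Step 3. Points that depend on Form 3, which is not in the documents.** If Q12c is left blank when there is no railing, an open stairwell matches no line, although section 10.2 names it as a hazard. Section 10.4.1 gives railing height only for stairwells that have one ("Height of stairwell railings (of those that had a railings"), which makes this worth checking. The unscored pattern Q12b = 1, Q12c > 0.9 m, Q12d = 2 matters only if it can occur. These are questions for the form, not established errors.

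**Step 4. Size.** The plan gives no figure to reproduce. A double-scored home differs by 1 on the 0-5 count, and each such home is 1/60 = 1.7% of the target sample. The number affected, k, is not in the documents, so a range is shown.

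Assumptions: p = k/60 homes are double-scored; c is the probability of an unambiguous stairwell score of 1 (0.05, 0.1, 0.2, 0.3); the other four items are independent with common prevalence q (0.1, 0.2, 0.3, 0.5); activity is linear in the correctly coded count. With V = 4q(1 − q):

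- Var0 = V + c(1 − c), ambiguous homes coded 0
- Var1 = V + (c + p)(1 − c − p), ambiguous homes coded 1
- Cov = V + c(1 − c − p)
- Correlation of the two counts = Cov/√(Var0 × Var1)
- Slope from the wrong coding as a fraction of the right one = Cov/Var0 or Cov/Var1, according to which coding is wrong

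Worked case, the least favourable slope at k = 3 (p = 0.05, c = 0.05, q = 0.1): V = 0.36; Cov = 0.36 + 0.05 × 0.90 = 0.405; Var1 = 0.36 + 0.10 × 0.90 = 0.45; slope ratio = 0.405/0.45 = 0.90.

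Minimum to maximum over the grid and both directions:

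| k of 60 | Correlation of counts | Slope ratio |
|---|---|---|
| 0 | 1.00 | 1.00 |
| 1 | 0.980-0.993 | 0.963-0.999 |
| 3 | 0.946-0.981 | 0.900-0.998 |
| 6 | 0.903-0.963 | 0.826-0.995 |
| 12 | 0.842-0.935 | 0.726-0.990 |

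This covers the double score only. A home at exactly 0.9 m has no count at all.

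**The case against.** The best counter-argument is that the lists themselves point to the intended reading. The two longer lines scoring 0 differ only in Q12d, so with Q12b = 2 and a height above 0.9 m the score seems meant to be 0 whatever Q12d is. If the third line scoring 1 took precedence, one of those lines could never operate; if the line scoring 0 took precedence, the third line would still operate where Q12b is not 2. On that view a Q12b condition was simply dropped.

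That is plausible but not decisive. It needs homes with Q12b other than 2 to have a height above 0.9 m. If Q12b = 2 merely records that a railing is present, no such home exists, and the third line would be the idle one. Deleting the overlapping line from the list scoring 0 is then just as natural a repair, and it gives the opposite score. The documents do not choose between them.

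The objections on weight largely stand. Most patterns score cleanly, and the construction, drain and boti items are untouched. The 0.9 m gap is a missing equals sign, and how finely heights are recorded is not stated. The count is one of six exposures listed in section 10.2, and stairwells and stove height are also described in their own right. For scale, assuming a true correlation of 0.3 with 60 independent children, the standard error of the slope is √((1 − 0.09)/58)/0.3, about 42% of the slope, so the coding effect at small k lies well inside sampling error. The larger values of k have no basis in the documents and serve only to show the range.

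**Conclusion.** The concern holds. Table 1 contradicts itself for one stairwell pattern and is silent at exactly 0.9 m for two items; neither finding depends on what the Form 3 codes mean, and no other section supplies a precedence or boundary rule. The consequence is confined to homes with those answers. Their number is unknown, may be small and could be zero. Under the stated assumptions the slope changes by at most about 4% for one double-scored home, 10% for three, 17% for six and 27% for twelve. The description of activity levels and the basis for 60 children are not touched. This should be corrected because the rule for a named exposure does not return a single score for these answers, not because a material effect on any result has been shown.

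**What to change.** Before the hazard count is related to activity, rewrite the stairwell entry in Table 1 from the Form 3 labels for Q12b and Q12d so that the two lists are mutually exclusive and cover every possible pattern:

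1. Put the double-scored pattern (Q12b = 2, height above 0.9 m, Q12d = 1) in one list only.
2. State the Q12b condition in every line that scores 1.
3. Assign exactly 0.9 m to one side, for both the stairwell and the stove item.
4. Confirm from Form 3 that a stairwell without a railing scores as a hazard, in line with section 10.2, and that every other possible pattern has one score. As a cross-check, the homes tabulated in section 10.4.1 under "Homes that had open stairwells (no railings" should have stairwell scores that agree.
5. Set an item to missing only if a needed answer is still absent after the re-collection step in section 10.4.1.
6. Report how many homes had the double-scored pattern. Rerunning the model with the other coding is optional.

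The cost is low: one rewritten table entry, using answers already collected. It needs no visits beyond the re-collection already planned, no change to the sample size and no additional required model.
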